Pre-test sessions will be conducted from a private location and participants will have the option to mute their own video (i.e., use only audio from their end) if they prefer to remain discreet. Sessions will be audio-recorded using a digital voice recorder to allow for the ongoing monitoring of intervention fidelity. No audio or video will be recorded in Zoom. The audio recordings will be transferred to a secure UM server immediately after the session, and then deleted from the digital voice recorder. The recordings will not be transcribed, but IRB-approved study team members will listen to them on an ongoing basis to identify and discuss areas of potential improvement. The recordings will be deleted from the UM server upon study completion (i.e., when all study-related data have been collected and checked for accuracy and completeness). During the session, the interventionist will follow procedures described in the pre-test intervention outline. The session will begin with a conversation to initiate a collaborative partnership and build rapport (MI process: *Engaging*). Next, the interventionist will elicit participants' awareness of the epidemiology and transmission of bacterial STIs among GBMSM-LWH, provide new information to fill any knowledge gaps or address misconceptions around triple-site GC and CT or syphilis

testing, and elicit reactions to this new information. Open-ended questioning and reflective listening will be used to gain a better understanding of participants' perspectives on their own sexual risk and protective behaviors (MI process: Focusing). Subsequently, the interventionist will explore their history of bacterial STI testing, their motivations for testing or reasons for not testing, and their perceived benefits and challenges of regular testing (MI process: Evoking). To improve self-efficacy for specimen self-collection, the interventionist will demonstrate the contents of the specimen self-collection box, review step-by-step instructions for self-collecting each type of specimen, and address any questions or concerns. Participants who express an intent to test with their own provider or at a clinic will be encouraged to pursue that route. The session will end by summarizing the participants' strengths and goals with respect to protecting their own and their partners' sexual health and discussing their plans to test for GC, CT, and syphilis over the next month (MI process: Planning).

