address). Only IRB-approved study team members at the UM will have access to the data on which unique specimen ID numbers are assigned to a particular participant ID number, and which participant ID number corresponds to a particular participant's contact information. These data will be stored in a password-protected file on a secure UM server. Before sending a link to the baseline survey to an individual whose contact information has been verified, a study team member will update the file containing participants' contact information with a corresponding participant ID number (e.g., ZEN618). Before shipping a specimen self-collection box to this participant, a study team member will further update the file with information on which unique specimen ID numbers affixed to the different transport tubes (e.g., URN327, THR327, REC327, BLD327) are assigned to their participant ID number. This file will be deleted from the UM server upon study completion (i.e., when all study-related data have been collected and checked for accuracy and completeness). GC, CT, and syphilis test results will be shared with us by lab personnel at CVRL via a secure Dropbox folder and will be stored on a secure UM server. Once we receive all the test results, lab personnel at CVRL will no longer have access to the folder.

Participants who do not return any specimens by the end of 8 weeks will be deemed not interested in this intervention component (unless they have requested an extension). Those who return some or all specimens within 8 weeks will proceed to the next intervention component.

Note: Dropbox is approved by the UM ITS for sensitive identifiable human subjects research data regulated by the "Common Rule". Access to the Dropbox account is protected with a sufficiently complex password and requires Duo two-factor authentication for login. Only IRB-approved study team members, all of whom will have completed trainings on human subjects research protections offered by the UM PEERRS, will have access to participants' data on an as-needed basis.

d. Intervention component III - Post-test MI-guided live AV conferencing session

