
For participants receiving a positive GC, CT, or syphilis test result, a study team member will review their state and local statutory reporting requirements and procedures and make up to 3 attempts to notify the relevant public health authorities. Reporting of these bacterial STIs can be performed without providing isolates. Participants' contact information will be reported. This notification may result in participants being contacted by their public health authorities for follow up and possible contact tracing. A study team member will also follow up via phone at 2 weeks and at 4 weeks to determine their treatment status. During each of these interactions, the study team member will complete a case report form programmed in Qualtrics documenting whether the participant has initiated treatment, completed treatment, has not yet initiated treatment but has made an appointment with a provider, or has not yet made an appointment with a provider. Those who have not yet made an appointment with a provider will be encouraged to do so as soon as possible and offered additional assistance as requested. The data entered into the case report forms will be downloaded to a secure UM server.

Participants who do not schedule or attend the post-test session will be deemed not interested in this intervention component (unless they have contacted us to reschedule). However, a copy of the lab test results form and the supplemental information sheet on using site locators to identify local STI clinics will be shared with these participants via a secure Dropbox folder that is only accessible to them and the study team members. The link to the folder will expire after 4 weeks and the folder will be deleted, following which participants will need to contact us to obtain a new link.

Note: Qualtrics, Zoom, and Dropbox are approved by the UM ITS for sensitive identifiable human subjects research data regulated by the "Common Rule". Access to the Qualtrics, Zoom, and Dropbox accounts is protected with a sufficiently complex password and requires Duo two-factor authentication for login. Only IRB-approved study team members, all of whom will have completed trainings on human subjects research protections offered by the UM PEERRS, will have access to participants' data on an as-needed basis.

e. Satisfaction survey

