Upon completion of the intervention delivery, all 75 "fully enrolled" participants (regardless of their level of engagement in the pre-test session, specimen return for bacterial STI testing, and the post-test session) will be sent a link to the satisfaction survey programmed in Qualtrics (with the participant ID number included as a metadata element) that will include questions on the following:

- (i) Pre-test live AV conferencing session experience: 4-item subscale from the Telehealth Usability Questionnaire to assess the participant's quality of interaction with the interventionist, 106 12-item Counselor Rating Form Short to assess the participant's perceptions of the interventionist, 107 5-point Likert items to assess the participant's satisfaction with, willingness to repeat, and likelihood to recommend the session.
- (ii) Urine sample self-collection experience: 5-point Likert items to assess the participant's experience with, willingness to repeat, and likelihood to recommend self-collection. 66
- (iii) Throat swab self-collection experience: 5-point Likert items to assess the participant's experience with, willingness to repeat, and likelihood to recommend self-collection. 66
- (iv) Rectal swab self-collection experience: 5-point Likert items to assess the participant's experience with, willingness to repeat, and likelihood to recommend self-collection. 66
- (v) Finger-stick blood sample self-collection experience: 5-point Likert items to assess the participant's experience with, willingness to repeat, and likelihood to recommend selfcollection.⁶⁶
- (vi) Specimen packaging and return experience: 5-point Likert items to assess the participant's experience with packaging and returning specimens.
- (vii) Post-test live AV conferencing session experience: 4-item subscale from the Telehealth Usability Questionnaire to assess the participant's quality of interaction with the interventionist, 106 12-item Counselor Rating Form Short to assess the participant's perceptions of the interventionist, 107 5-point Likert items to assess the participant's satisfaction with, willingness to repeat, and likelihood to recommend the session.
- (viii) Bacterial STI-related knowledge: 22-item scale to assess the participant's knowledge of GC, CT, and syphilis⁹⁸ for comparison with the baseline survey responses.

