- (ix) Likelihood of testing for bacterial STIs in the future: 5-point Likert items to assess the participant's likelihood of testing for bacterial STIs at least annually and likelihood of using home STI tests sold online by companies.

The satisfaction survey should take approximately 30 min to complete, and it will allow participants to skip questions or indicate that they prefer not to answer a question. If participants do not complete the satisfaction survey within 1 week, up to 7 reminders will be sent at regular intervals over the next 7 weeks. The reminders will inform participants that non-completion of the satisfaction survey by the end of 8 weeks suggests that they are no longer interested (unless they request an extension). Those who complete the satisfaction survey will receive a \$20 Amazon egift card.

Note: Qualtrics is approved by the UM ITS for sensitive identifiable human subjects research data regulated by the "Common Rule". Access to the Qualtrics account is protected with a sufficiently complex password and requires Duo two-factor authentication for login. The data collected via the satisfaction survey will be downloaded to a secure UM server. Only IRB-approved study team members, all of whom will have completed trainings on human subjects research protections offered by the UM PEERRS, will have access to participants' data on an as-needed basis.

Section 4. Phase 2 procedures

To gain a deeper understanding of attitudes, facilitators, and barriers related to engaging in each component of the intervention, we will conduct in-depth interviews with a subsample of 20 participants. Purposive sampling will be used to select a mix of participants who complete progressively smaller subsets of the pre-test session, specimen return for bacterial STI testing, and the post-test session. 108

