Participants will be contacted to schedule a 1-hour interview with a study team member to be conducted over Zoom or phone (depending upon their preference). Time slots will be offered in all US time zones and be flexible to meet their individual circumstances. If participants do not schedule an interview within 1 week, up to 7 reminders will be sent at regular intervals over the next 7 weeks. The reminders will inform participants that not scheduling an interview by the end of 8 weeks suggests that they are no longer interested (unless they request an extension). Participants who prefer being interviewed over Zoom will be sent a password-protected Zoom link. They will be advised to join the interview from a private location and be offered the option to reschedule if the original time no longer works or if they anticipate being in a situation where their privacy may be compromised.

Interviews will be conducted from a private location and participants on Zoom will have the option to mute their own video (i.e., use only audio from their end) if they prefer to remain discreet. Interviews will be audio-recorded using a digital voice recorder to allow for verbatim transcription. No audio or video will be recorded in Zoom. The audio recordings will be transferred to a secure UM server immediately after the interview, and then deleted from the digital voice recorder. During the interview, the study team member will ask participants open-ended questions outlined in the semi-structured in-depth interview guide. Informed by the TFA of health interventions⁷⁴, the interviews will focus on a range of participants' experiences including factors influencing their attendance (e.g., discuss specimen self-collection procedures, receive bacterial STI test results) or non-attendance (e.g., concerns about session length, scheduling conflicts) of the pre-test or the post-test sessions, and reasons for returning specimens (e.g., confirm bacterial STI status, limited access to testing) or choosing not to return specimens (e.g., lack of confidence, preference for clinic-based testing). The audio recordings will be transcribed by IRB-approved study team members, all of whom will have completed trainings on human subjects research protections offered by the UM PEERRS. Each transcript will only be connected to the participant ID number and saved on a secure UM server. The recordings will be deleted from the UM server upon study

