Descriptive statistics (e.g., means, medians and ranges for continuous variables, counts and proportions for categorical variables) and progression ratios (i.e., proportions who sequentially progress through different intervention components) will be calculated using software for quantitative data analysis (e.g., SAS, Excel). Intervention feasibility outcomes include the number of participants who (i) schedule a pre-test session, (ii) join the pre-test session within 15 min of the start time, (iii) return each type of specimen, (iv) provide specimens of adequate quality for lab testing, (v) schedule a post-test session, and (vi) join the post-test session within 15 min of the start time. Intervention acceptability outcomes include (i) satisfaction with the different intervention components, (ii) willingness to repeat the different intervention components, (iii) willingness to recommend the different intervention components to friends or sex partners, (iv) quality of interactions with and perception of the interventionist, and (v) comparison of bacterial STI testing experience in the study with the last testing experience. Potential impact of the intervention on IMB model constructs will be assessed by calculating (i) improvement in bacterial STI-related knowledge, (ii) willingness to test for bacterial STIs at least annually, and (iii) improvement in self-efficacy for specimen self-collection. Because our study is inherently exploratory, we do not plan on using probability-based statistical inference techniques in line with current best practices. 109, 110 Instead, potential variations in our intervention's feasibility and acceptability across selected participant characteristics, and its potential impact on IMB model constructs will be numerically summarized and graphically visualized (e.g., side-by-side boxplots, scatter plots), as recommended for exploratory data. 111, 112 Proportions of participants who test negative or positive for GC, CT, and syphilis (using our specimen self-collection kits or with their own provider or at a clinic), and proportions who initiate treatment (with their own provider or at a clinic or via commercial telehealth services) within 2 weeks or 4 weeks of receiving a positive test result will also be calculated.

b. Phase 2 analyses

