- (iii) Improvement in self-efficacy for specimen self-collection: Potential increases in participants' self-efficacy for urine sample self-collection, throat swab self-collection, rectal swab self-collection, and finger-stick blood sample self-collection will be assessed by comparing responses to similar sets of four 5-point Likert items included in the baseline survey and the satisfaction survey. Response values will be summed to obtain separate total scores ranging from 4-20, with higher scores indicating greater self-efficacy for specimen self-collection.

Outcomes to measure the prevalence of bacterial STIs and receipt of treatment include the following:

- (i) Number of participants that test negative or positive for GC, CT, and syphilis (using our specimen self-collection kits or with their own provider or at a clinic).
- (ii) Number of participants that initiate treatment (with their own provider or at a clinic or via commercial telehealth services) within 1 week of receiving a positive test result.

Because our study is inherently exploratory, we do not plan on using probability-based statistical inference techniques in line with current best practices. ^{109, 110} Instead, potential variations in our intervention's feasibility and acceptability across selected participant characteristics, and its potential impact on IMB model constructs will be numerically summarized and graphically visualized (e.g., side-by-side boxplots, scatter plots), as recommended for exploratory data. ^{111, 112}

Ame00145753

Instead of using a bubble mailer for participants to return their specimens, we will be using a shipping box made of cardboard as the outer shipping package. This change is to promote compliance with the Hazardous Materials Regulations for the safe transportation of hazardous materials, including Category B infectious substances, that recommend the use of "rigid outer packaging" (HMR; 49 CFR §173.199). To reflect this change, we have replaced the phrase "bubble mailer" with "shipping box" in the informed consent form and have updated the general information sheet that includes packaging instructions for participants. We have also included our contact details in the general information sheet and the supplemental information sheet so that

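### The test-result outcome counts provider and clinic tests, but no instrument described after baseline collects the results of tests done outside the study

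*Combined protocol and SAP*

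**What the plan says.** Section 5.a (Phase 1 analyses) defines the test-result outcome as a proportion for those "who test negative or positive for GC, CT, and syphilis (using our specimen self-collection kits or with their own provider or at a clinic". It thus has two sources: the study's own kits, and tests obtained in ordinary care. The amended Section 5.a under Ame00143150 labels it a secondary outcome and keeps both sources, now as a count of those "that test negative or positive for GC, CT, and syphilis (using our specimen self-collection kits or with their own provider or at a clinic".

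The plan expects the second source to exist. In the pre-test session (Section 3.b), "Participants who express an intent to test with their own provider or at a clinic will be encouraged to pursue that route". The same section adds that these participants are nevertheless sent a kit once the session is complete, unless they withdraw. Under Section 3.c, returning specimens is voluntary and may be complete, partial or nil. Section 4, on the interviews, gives examples of reasons for not returning a kit: "or choosing not to return specimens (e.g., lack of confidence, preference for clinic-based testing".

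**The concern.** An outcome with two stated sources needs a route by which each reaches the dataset. The kit route is described in detail. For tests done elsewhere during the study, no route is described.

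What is at stake is the meaning of a missing result. A participant who took the advice to use a clinic and mailed nothing back would have the same record as one who was never tested. Results that participants happened to volunteer could enter the count, but they would come mainly from people who still had scheduled contact with staff, namely kit returners and those followed up after a positive result. The outcome on starting treatment begins from the same set of positives, so it inherits the gap. If the information is not asked for while the study is running, it cannot be recovered at analysis.

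**Working it through.** No arithmetic decides this point, and the plan gives no figure to reproduce. The check is to follow the outcome through each described source and ask whether it could hold the result of a GC, CT or syphilis test done outside the study after the baseline survey.

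1. **Baseline survey (Section 3.a, item ix).** It asks when and where the most recent tests were done, which specimens were given, what they showed and whether treatment followed. This is the right content, but the survey must be completed before the intervention starts. It can hold results from before enrolment. It cannot hold tests prompted by the later pre-test session.
2. **Laboratory file (Section 3.c).** It holds results keyed to the specimen numbers on the study's transport tubes, so it covers study specimens only.
3. **Post-test session (Section 3.d).** Access depends on returning something: "Those who return some or all specimens within 8 weeks will proceed to the next intervention component". Someone who tests only elsewhere does not reach it. Someone who returns part of the kit does, and could mention, say, a clinic syphilis test. However, the described session content has no step for recording this, and the audio is kept for fidelity monitoring and not transcribed.
4. **Case report form (Section 3.d).** It is completed by phone at 2 and 4 weeks for participants with a positive result, "documenting whether the participant has initiated treatment, completed treatment, has not yet initiated treatment but has made an appointment with a provider"; the remaining category is no appointment so far. It records treatment status, and has no described field for an outside test or its result.
5. **Satisfaction survey (Section 3.e).** It is sent to everyone who is fully enrolled (75 people), "regardless of their level of engagement in the pre-test session, specimen return for bacterial STI testing, and the post-test session", so it has the right reach. The listed topics are experience of the sessions and kits, packaging and return, STI knowledge, and finally "Likelihood of testing for bacterial STIs in the future: 5-point Likert items to assess". That last topic looks forward. None of the listed topics asks what was done elsewhere since baseline.
6. **Interviews (Section 4).** They involve a purposive 20 of 75 participants (20/75 = 26.7%), cover experiences and reasons, and are analysed thematically. They are not a source of results for the whole sample.

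The trace gives three answers. Kit results have a described source. Outside results from before enrolment have one, by self-report. Outside results from after baseline have none.

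**The case against.** The strongest reply is that the documents list survey topics and do not reproduce the questionnaires, and that the lists are visibly abbreviated. The amended Section 5.a scores satisfaction with each type of specimen collection from the satisfaction survey, while Section 3.e lists only experience, willingness to repeat and likelihood to recommend for specimens. Section 5.a also plans a comparison with the participant's last testing experience that no listed topic names. Absence from the list therefore does not prove absence from the survey. This stands, and it limits the point to the plan as described. If the item already exists, naming it in the plan settles the matter.

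A second reply is that encouragement to test elsewhere does not replace the kit, because the box is shipped anyway. This also stands. It narrows the affected group to people who test outside and return no usable kit specimen for that infection, but it does not empty the group, because return is voluntary.

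A third reply is that non-returners are not abandoned: they receive up to 5 specimen reminders, then the satisfaction survey with up to 7 more. That is true, but nothing in the described reminders or survey topics asks for outside results.

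Three stronger readings are tempting and are not supported. A reader might infer that no form at all collects provider or clinic results; baseline item ix does, for tests before enrolment. A reader might take the list of Qualtrics forms in Section 6.b as proof that no other record exists; that sentence says what will be deleted from Qualtrics and is not an inventory of data sources. Session attendance and specimen quality, for example, are not attributed to any form there. A reader might also want a range for the error in the proportion positive; the documents give neither the number with kit results nor the number testing only elsewhere, so any such range would rest on invented inputs.

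**Conclusion.** The concern holds for tests done outside the study after the baseline survey. Followed as described, the plan can fill this outcome systematically only from kit results, and it cannot separate participants who tested only elsewhere from those who did not test.

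The number affected is unknown. It may be zero, and for each infection it cannot exceed the number of participants without a kit result. The outcome is secondary and descriptive, no inference is planned on it, and prevalence is not part of either specific aim. The primary feasibility and acceptability outcomes do not depend on it. The conclusion rests on one assumption: that the unseen questionnaires contain no relevant item beyond their listed topics. This is an inexpensive improvement to data collection, and it does not threaten the study's main findings.

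**What to change.** Add to the satisfaction survey the questions of baseline item ix, limited to GC, CT and syphilis tests done outside the study since the baseline survey: date, site, specimen types, result and treatment. In Section 5.a, report kit results and self-reported outside results in separate rows, each with its own denominator, together with the number of participants who have neither.

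If the questions are not added, restrict the outcome to kit results and delete the provider and clinic wording.

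The cost is a few more questions in a survey of about 30 minutes, some extra table rows and an IRB amendment. Anyone who has already completed the survey would need a short follow-up question or be listed as not asked. The outside results would be self-reported and would depend on survey response, which is the reason not to pool them with laboratory results. Laboratory procedures do not change.
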